9.1.7 Response in Non-Measurable Lesions (RECIST 1.1)

While some non-target lesions may actually be measurable, they need not be measured and instead should be assessed only qualitatively.

- Complete Response (CR): Disappearance of all non-target lesions and normalization of tumor marker level. All lymph nodes must be non-pathological in size (<10mm short axis).
- Non-CR/Non-PD: Persistence of one or more non-target lesion(s) and/or maintenance of tumor marker level above the normal limits.
- Progressive Disease (PD): Unequivocal progression of existing non-target lesions. (Note: the appearance of one or more new lesions is also considered progression).

When the subject also has measurable disease, to achieve 'unequivocal progression' on the basis of non-target disease, there must be an overall level of substantial worsening in non-target disease such that, even in presence of SD or PR in target disease, the overall tumor burden has increased sufficiently to merit discontinuation of therapy.

In the event that the subject has only non-measurable disease, the same general concepts apply as noted above, however, in this instance there is no measurable disease assessment to factor into the interpretation of an increase in non-measurable disease burden. Because worsening in non-target disease cannot be easily quantified, a useful test that can be applied when assessing subjects for unequivocal progression is to consider if the increase in overall disease burden based on the change in non-measurable disease is comparable in magnitude to the increase that would be required to declare PD for measurable disease (i.e., an increase in tumor burden representing an additional 73% increase in 'volume' which is equivalent to a 20% increase diameter in a measurable lesion).

9.1.8 Immune-Related Response in Non-Measurable Lesions

At each tumor assessment, the presence of any new, non-measurable lesions is assessed. The presence of such lesions will rule out an overall response of irCR. An increase in the size or number of new, non-measurable lesions does not necessarily imply an overall response of irPD; if these lesions become measurable (≥ 10 mm) at a subsequent tumor assessment, their measurement will at that point start to contribute to the TMTB.

In addition, the response in non-target lesions is defined as follows:

- Complete Response (irCR): complete disappearance of all non-target lesions
- Stable Disease (irSD): non-target lesions are stable
- Progressive Disease (irPD): unequivocal increases in number or size of non-target lesions. To achieve unequivocal progression of non-target lesions, there must be an overall level of substantial worsening of non-target disease that is of a magnitude that the treating physician would feel it is important to change therapy.

NOTE: Equivocal findings of progression of non-target lesions (e.g., small and uncertain new lesions; cystic changes or necrosis in existing lesions) should be considered irSD, and treatment may continue until the next scheduled assessment.

9.1.9 Overall Response

Overall response will be determined based on RECIST 1.1 criteria and by irRECIST criteria (Table 6). Overall response according to irRECIST is derived from the responses in measurable lesions (based on TMTB) and the presence of any non-measurable lesions.

Table 6 Tumor Response Evaluation: Comparison of RECIST 1.1 and irRECIST

Criteria	RECIST 1.1	irRECIST
New measurable lesions (≥ 10 mm)	Always represents PD	Incorporated into tumor burden
New non- measurable lesions (< 10 mm)	Always represents PD	Does not define progression but precludes irCR
Non-Target lesions	Changes contribute to defining BOR of CR, PR, SD, and PD	Contribute to defining irCR (complete disappearance required)
CR	Disappearance of all lesions	Disappearance of all lesions
PR	≥ 30% decrease in the sum of the longest diameter of all target lesions compared with baseline, in absence of new lesions or unequivocal progression of non-target lesions	≥ 30% decrease in tumor burden compared with baseline

Criteria	RECIST 1.1	irRECIST
SD	Neither sufficient shrinkage to qualify for PR nor sufficient increase to qualify for PD, taking as reference the smallest sum diameters while on study	Neither a 30% decrease in tumor burden compared with baseline nor a 20% increase compared with nadir can be established
PD	At least 20% increase in sum of diameters of target lesions, taking as reference the smallest sum on study. In addition to the relative increase of 20%, the sum must also demonstrate an absolute increase of at least 5mm. The appearance of one or more new lesions is also considered progression.	At least 20% increase in tumor burden compared with nadir (at any single time point) ^a

irRECIST = immune-related Response Evaluation Criteria in Solid Tumors; BOR = best overall response; CR = complete response; irCR = immune-related complete response; PD = progressive disease; PR = partial response; SD = stable disease;

9.1.10 Best Overall Response (RECIST 1.1)

The best overall response is the best response recorded from the start of the study treatment until the end of treatment taking into account any requirement for confirmation. The subject's best overall response assignment will depend on the findings of both target and non-target disease and will also take into consideration the appearance of new lesions (Table 7).

Table 7 Best Overall Response (RECIST 1.1)

Target Lesions	Target Lesions Non-Target Lesions		
Baseline (Index) and New Measurable Lesions	Baseline Lesions	Baseline Lesions Unequivocal New Lesions	
CR	CR	No	CR
CR	Non-CR/Non-PD	No	PR
CR	NE	No	PR
PR	Non-PD or NE	No	PR
SD	Non-PD or NE	No	SD
Not all evaluated	Non-PD	No	NE
PD	Any	Yes or No	PD
Any	PD	Yes or No	PD

a Subjects with an initial finding of progressive disease (irPD) before or at the 12-week imaging assessment, but without rapid clinical deterioration, require confirmation of irPD with a second, consecutive scan obtained ≥ 4 weeks from the initiation documentation. Subjects will continue to receive study treatment until irPD is confirmed at this later time point. Best overall response (BOR) will therefore include responses occurring at any time before disease progression and after early progression (i.e., within the first 12 weeks of the study).

Target Lesions	Non-Target Lesions		
Baseline (Index) and New Measurable Lesions Baseline Lesions		Unequivocal New Lesions	Overall Response
Any	Any	Yes	PD

CR = complete response; NE = not evaluable at a particular time point; PR = partial response; SD = stable disease; PD = progressive disease

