9.1.11 Immune-Related Best Overall Response (irRECIST)

The immune-related best overall response (irBOR) is the best irRC overall response over the study as a whole, recorded between the date of first dose until the last tumor assessment prior to subsequent therapy (including tumor resection surgery) for the individual subject in the study (Table 8). As with the primary definitions of tumor response, early progression (i.e., irPD occurring prior to Week 12) will not preclude an irBOR of irCR, irPR or irSD resulting from the Week 12 assessment. An assessment of irPD at or after Week 12 will preclude a subsequent irBOR of irCR, irPR or irSD. However, any post-progression clinical activity in subjects with irBOR of irPD may be summarized for exploratory purposes.

Table 8 Immune-Related Best Overall Response (irBOR)

Target Lesions Baseline (Index) and New Measurable Lesions Non-Target I		Lesions ^a	
Total Measurable Tumor Burden	Baseline Lesions	Unequivocal New Lesions	irRC Overall Response
irCR	irCR	No	irCR
irCR	irSD	No	irPR
irPR	irCR or irSD	No	irPR
irSD	irCR or irSD	No	irSD
irPD	Any	Yes or No	irPD
Any	Unequivocal Progression	Yes or No	irPD
Any	Any	Yes	irPD

irCR = immune-related complete response; irPR = immune-related partial response; irSD = immune-related stable disease; irPD = immune-related progressive disease

^a Any increase in the size or number of non-measurable lesions does not necessarily imply an overall response of irPD. If these lesions become measurable (≥10 mm) at a subsequent assessment, their measurement will at that point start to contribute to the total measurable tumor burden. To achieve unequivocal progression of non-target lesions, there must be substantial worsening in non-target disease that is of a magnitude that the Investigator feels it is important to change therapy. Equivocal findings of progression of non-target lesions (e.g., small and uncertain new lesions; cystic changes or necrosis in existing lesions) should be considered irSD, and treatment may continue until the next assessment.

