9.1.12 Treatment after Initial Evidence of Radiologic Disease Progression

Immunotherapy may produce antitumor effects by potentiating endogenous cancerspecific immune response. The response patterns seen with such an approach may extend beyond the typical time course of responses seen with cytotoxic agents and can manifest as a clinical response after an initial increase on tumor burden or even the appearance of new lesions. If radiological imaging shows PD, subjects may continue on study with the option of continuing treatment, provided there is:

- No deterioration in ECOG performance status
- Absence of signs and symptoms (including worsening of laboratory values) indicating disease progression
- Absence of rapid progression of disease
- Absence of progressive tumor at critical anatomical sites (e.g., cord compression) requiring urgent alternative medical intervention

Tumor assessment should be repeated ≥4 weeks later to confirm PD. If repeat imaging shows a reduction of in the tumor burden demonstrating CR, PR or SD compared to the initial scan, treatments may be continued or resumed. If repeat imaging shows continued progression of disease, subjects will be discontinued from study therapy, unless the basis for the PD assessment is enlarged tumor-draining lymph nodes in the presence of a target tumor reduction. In determining whether or not tumor burden has increased or decreased, investigators should consider all target lesions as well as non-target lesions. If the repeat imaging confirms initially documented PD but shows no evidence of further tumor progression, subjects should be discontinued from the study treatment.

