14.5.5 Analysis of Efficacy

All subjects who complete at least one cycle of ADXS11-001 treatment will be included in the efficacy analyses. The following are efficacy parameters for the study:

- 1. Objective Response Rate (ORR)
- 2. Duration of tumor response
- 3. Stable Disease Rate (proportion of CR, PR, SD)
- 4. Duration of Stable Disease (SD)
- 5. Progression free survival (PFS)

Tumor response will be evaluated by RECIST 1.1 and irRECIST criteria. The ORR will be calculated as the proportion of subjects who achieved CR/irCR or PR/irPR. The duration of response is defined as the time interval from CR/irCR or PR/irPR to disease progression or death. If the subject's disease remains responsive by the time of discontinuation or completion of the study, the duration will be censored at that time point. The stable disease rate will be calculated as the proportion of subjects who achieved CR/irCR, PR/irPR or SD/irSD. The duration of SD is defined as the time interval from CR/irCR or PR/irPR or SD/irSD to disease progression or death. If the subject's disease remains stable by the time of discontinuation or completion of the study, the duration will be censored at that time point.

PFS is defined as the time interval from first infusion of study treatment to disease progression or death. If the subject's disease has not progressed by the time of discontinuation or completion of the study, the PFS will be censored at that time point.

Efficacy parameters will be descriptively summarized by dose cohorts as well as for all cohorts combined. Tumor response will be summarized according to response category. Response rate and stable disease rate will be summarized by frequency table. For durations of response and SD/irSD as well as PFS, the Kaplan-Meier method will be used to estimate the median times. Descriptive statistics and Kaplan-Meier curves will be presented.

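### RECIST 1.1 best overall response has no explicit cut at first PD, so a RECIST progression that later reverses can be scored as a RECIST response or stable disease

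*Combined protocol and SAP*

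**What the plan says.** **RECIST best overall response (9.1.10).** "The best overall response is the best response recorded from the start of the study treatment until the end of treatment". The sentence goes on to allow for confirmation requirements but does not say which. No cut at progression is stated.

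**Treatment after PD (9.1.12).** "If radiological imaging shows PD, subjects may continue on study with the option of continuing treatment, provided there is" four clinical conditions. If the repeat scan, at least 4 weeks later, shows reduced tumor burden "demonstrating CR, PR or SD compared to the initial scan, treatments may be continued or resumed". Treatment ends on continued progression, except where the PD rests on enlarged tumor-draining lymph nodes while target tumor shrinks. It also ends on a confirmed but static PD: "If the repeat imaging confirms initially documented PD but shows no evidence of further tumor progression, subjects should be discontinued from the study treatment".

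**Immune-related best overall response (9.1.11).** "An assessment of irPD at or after Week 12 will preclude a subsequent irBOR of irCR, irPR or irSD". Section 9.1.10 has no matching sentence.

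**Footnote a to Table 6.** "Best overall response (BOR) will therefore include responses occurring at any time before disease progression and after early progression", where early means the first 12 weeks. The marker sits in the irRECIST PD cell and the note speaks of irPD, but this sentence says BOR rather than irBOR.

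**Efficacy analysis (14.5.5).** ORR is the proportion who achieved CR/irCR or PR/irPR, and the stable disease rate adds SD/irSD. Neither requires the response to precede progression. "The duration of response is defined as the time interval from CR/irCR or PR/irPR to disease progression or death". PFS runs from first infusion to progression or death.

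**The concern.** A response window that closes at the end of treatment does no harm if treatment always ends at progression. Here it need not, because Section 9.1.12 keeps treatment open past an initial PD. Section 9.1.6 presents irRECIST as the adaptation that tolerates apparent progression, so one would expect RECIST 1.1 to be the stricter of the two. On late progression the text makes it the looser one.

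At stake are the RECIST ORR, the stable disease rate, the two durations, and the meaning of the RECIST versus irRECIST comparison. If the RECIST PFS event is dated at the first PD, the same subject can be a PFS event and afterwards a RECIST responder, with a response that begins after progression.

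**Working it through.** The plan gives no target ORR, alpha, power or derived sample size, so there is no figure of its own to reproduce. The check applies its rules to example target sums.

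**Rules (9.1.5).** PR: sum at least 30% below baseline. PD: sum at least 20% above the smallest sum on study and at least 5 mm larger; any new lesion is also PD. SD: neither. Table 7 combines target, non-target and new-lesion findings at one time point (its NE is defined at a particular time point), so it does not carry an earlier PD forward.

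**Example A, clear of the Week 12 boundary.** Baseline 50 mm, no new lesions, non-target disease stable.

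| Scan | Sum (mm) | Arithmetic | RECIST 1.1 |
|---|---|---|---|
| Week 12 | 50 | 0% | SD |
| Week 24 | 62 | 62/50 = +24%, +12 mm over smallest sum | PD |
| Repeat scan | 55 | 55/50 = +10% over smallest sum | SD |
| Week 36 | 34 | 34/50 = -32% from baseline | PR |

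- The repeat scan shows SD, so 9.1.12 allows treatment to go on and the 9.1.10 window stays open. RECIST BOR as written is PR.
- With a cut at first PD, BOR is SD, from Week 12.
- Under irRECIST the Week 24 rise is also 24% over nadir. If it is scored as irPD, 9.1.11 bars a later irPR.
- If PFS is dated at first PD, its event falls at Week 24 and the response starts at Week 36, 36 - 24 = 12 weeks later.

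**Example B, PD at the first scan.** Baseline 50 mm, Week 12 62 mm (PD), repeat scan 55 mm (SD), no further shrinkage. BOR is SD as written and PD with a cut. In Example A the stable disease rate is unchanged, because the Week 12 SD already counts. That rate therefore moves mainly when PD is the first evaluable assessment, which is where footnote a and the confirmation wording make the rule unclear.

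**Example C, new lesions.** Sums 45, 34, 30 mm on a baseline of 50 mm. If a new lesion persists, every visit is PD and BOR is PD either way. If it has gone by the second scan, the visits are PD, PR, PR: BOR is PR as written and PD with a cut.

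**Size per affected subject = 100/n points.**
- n = 15 (the approximate number planned at the RP2D): 100/15 = 6.7. For example 2/15 = 13.3% becomes 3/15 = 20.0%.
- n = 12 (an illustration of fewer subjects completing a cycle): 100/12 = 8.3.
- n = 18 to 21 (my assumption for all cohorts combined: 15 plus 3 to 6 at another level): 100/18 = 5.6 to 100/21 = 4.8.

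**Frequency.** This is not in the documents. If a proportion p of subjects were affected, the expected inflation would be 100p points, and the chance of at least one such subject among 15 would be 1 - (1 - p)^15:

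| Assumed p | Expected inflation (points) | Chance of at least one in 15 |
|---|---|---|
| 2% | 2 | 26% |
| 5% | 5 | 54% |
| 10% | 10 | 79% |

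**The case against.** **Confirmation.** Section 9.1.10 allows for confirmation requirements, and Table 5, 8.1 and 8.3 ask for early apparent progression to be confirmed without naming a criterion. An early PD that is not confirmed could then be set aside under RECIST too. This is arguable for early PD. But 9.1.6 lists confirmation of progression among the differences between irRECIST and RECIST, and those three requests cover only the first 12 weeks. Section 9.1.12 asks for a repeat scan at any time, but as a rule for continuing treatment; it does not say that an unconfirmed PD is removed from RECIST BOR. Example A is not resolved.

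**Footnote a.** If it governs RECIST BOR, it may supply the missing rule: responses before progression count, with a deliberate exception for early progression. The reference in 9.1.11 to the primary definitions of tumor response lends this some support. But the note is attached to the irRECIST cell and concerns irPD, so its reach is unclear. It also treats irPD found at the 12-week scan as early, whereas 9.1.11 treats only irPD preceding Week 12 as early. An example with PD exactly at Week 12 would therefore prove little.

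**Stronger readings a reader might infer.**
- That any shrinkage after RECIST PD becomes a response. It does not: persisting new lesions stay PD under Table 7, and confirmed or continued progression ends treatment, apart from the lymph-node exception.
- That the plan itself dates PFS at an unconfirmed first PD and so contradicts its own ORR. It does not fix that date: 14.5.5 says disease progression and the synopsis says objective tumor progression.
- That ORR is shown to be inflated, or not comparable with other trials. The first needs a frequency and the second outside sources; the documents give neither.

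**Importance.** ORR is secondary and descriptive, and the RP2D rests on the DLT rate. At n = 15 the exact 95% intervals are 1.7% to 40.5% for 2/15 and 4.3% to 48.1% for 3/15, so one subject moves the estimate well within its own uncertainty. This stands, and it limits the weight of the point.

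**Conclusion.** The point holds in this limited form. The stated RECIST 1.1 rule can score a PR, or where no earlier SD exists an SD, after a RECIST PD that reverses: target or non-target growth that regresses, or a new lesion that disappears. For PD after Week 12 neither the confirmation wording nor footnote a clearly closes the gap, and RECIST is then looser than irRECIST if irPD is scored at that visit. This is a rule that can give the wrong classification, not merely a missing detail.

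The direction is certain: RECIST ORR and stable disease rate can only be equal to or higher than with a cut at first PD. The size is 1/n per affected subject, 6.7 points if 15 are evaluable and more if fewer complete a cycle. The total inflation cannot be derived, because the frequency of reversal after PD is not given; the 2% to 10% range is an assumption. No error rate, sample size or dose decision is affected. Still, Section 6 says that the expansion is meant to define efficacy further, and one or two reclassified subjects would visibly change the reported activity.

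**What to change.** - **9.1.10 and 14.5.5:** base RECIST 1.1 BOR, ORR, stable disease rate, duration of response and duration of SD on assessments up to and including the first RECIST 1.1 PD or the start of subsequent anticancer therapy, whichever comes first. Use the same PD date for RECIST PFS.
- **Footnote a and the confirmation wording:** limit both, for endpoint purposes, to irRECIST.
- **Week 12 boundary:** reconcile footnote a with 9.1.11 on whether irPD found at the 12-week scan counts as early.
- **Shrinkage after RECIST PD:** report it only under irRECIST, where its rules allow, or as exploratory.

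The cost is a few sentences and one programming rule. The downside is that RECIST ORR may come out slightly lower. The rules on continuing treatment and the scan schedule are untouched.

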9.1.11 Immune-Related Best Overall Response (irRECIST)

The immune-related best overall response (irBOR) is the best irRC overall response over the study as a whole, recorded between the date of first dose until the last tumor assessment prior to subsequent therapy (including tumor resection surgery) for the individual subject in the study (Table 8). As with the primary definitions of tumor response, early progression (i.e., irPD occurring prior to Week 12) will not preclude an irBOR of irCR, irPR or irSD resulting from the Week 12 assessment. An assessment of irPD at or after Week 12 will preclude a subsequent irBOR of irCR, irPR or irSD. However, any post-progression clinical activity in subjects with irBOR of irPD may be summarized for exploratory purposes.

Table 8 Immune-Related Best Overall Response (irBOR)

Target Lesions Baseline (Index) and New Measurable Lesions Non-Target I		Lesions ^a	
Total Measurable Tumor Burden	Baseline Lesions	Unequivocal New Lesions	irRC Overall Response
irCR	irCR	No	irCR
irCR	irSD	No	irPR
irPR	irCR or irSD	No	irPR
irSD	irCR or irSD	No	irSD
irPD	Any	Yes or No	irPD
Any	Unequivocal Progression	Yes or No	irPD
Any	Any	Yes	irPD

irCR = immune-related complete response; irPR = immune-related partial response; irSD = immune-related stable disease; irPD = immune-related progressive disease

^a Any increase in the size or number of non-measurable lesions does not necessarily imply an overall response of irPD. If these lesions become measurable (≥10 mm) at a subsequent assessment, their measurement will at that point start to contribute to the total measurable tumor burden. To achieve unequivocal progression of non-target lesions, there must be substantial worsening in non-target disease that is of a magnitude that the Investigator feels it is important to change therapy. Equivocal findings of progression of non-target lesions (e.g., small and uncertain new lesions; cystic changes or necrosis in existing lesions) should be considered irSD, and treatment may continue until the next assessment.

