- Baseline tumor imaging and assessments must be performed within 28 days prior to the first ADXS11-001 infusion in the first study cycle. Subsequent tumor imaging and assessments will be conducted at Week 12 (±1 week) for the duration of study participation. Apparent progression within the first 12 weeks, not accompanied by clinical deterioration, should be confirmed ≥4 weeks later.
- Immune monitoring/T-cell samples will be collected immediately prior to each ADXS11-001 infusion (Day 1 of Weeks 1, 4, 7, and 10) and between 11-14 days after every ADXS11-001 infusion in Cycle 1 only.
- Cytokine samples will be collected **in Cycle 1 only** at 3 time points immediately prior to each ADXS11-001 infusion and 2 hours and 4 hours post infusion (±15 minutes- Day 1 of Weeks 1, 4, 7, and 10).

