8.3 Study Cycle Evaluation

Baseline imaging studies and tumor assessments must be performed within 28 days prior to the first ADXS11-001 infusion in the first Treatment Period. Subsequent assessments will be conducted at Week 12 in Cycle 1, followed by assessment every 12 weeks (± 1 week) thereafter. Apparent progression within the first 12 weeks not accompanied by clinical deterioration, should be confirmed 3 to 4 weeks later.

Blood samples for immune monitoring and cytokine/chemokine analysis should be collected per schedule in Cycle 1 only (See Section 8.1 Study Procedures).

A physical examination, an ECOG Performance Status, vital sign measurements, hematology and chemistry profiles, and urinalysis will be performed prior to each study treatment infusion and at the end of therapy. Subjects will also be asked about the occurrence of any AEs and changes to concomitant medications.

Vital signs (including blood pressure, pulse rate, respiratory rate, and temperature) will be checked and recorded prior to administration of ADXS11-001 and following the infusion. Weight will be collected prior to each ADXS11-001 infusion.

A urine pregnancy test will be performed within 72 hours prior to each ADXS11-001 infusion and at the end of therapy for all women of childbearing potential.

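### Section 9.1.11 makes irPD at the Week 12 scan final for irBOR, while Table 6 footnote a requires the same finding to be confirmed first

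*Combined protocol and SAP*

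**What the plan says.** Section 9.1.11 defines the immune-related best overall response (irBOR). Its exemption reads: "early progression (i.e., irPD occurring prior to Week 12) will not preclude an irBOR of irCR, irPR or irSD resulting from the Week 12 assessment". The next sentence sets the limit: "An assessment of irPD at or after Week 12 will preclude a subsequent irBOR of irCR, irPR or irSD". Activity seen after that point may be summarised, but only as exploratory.

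Footnote a to Table 6 (Section 9.1.9) is attached to the irRECIST cell for progressive disease, although it prints under Section 9.1.10 beside Table 7. It says: "Subjects with an initial finding of progressive disease (irPD) before or at the 12-week imaging assessment, but without rapid clinical deterioration, require confirmation of irPD", by a second consecutive scan at least 4 weeks after the scan that showed it, with study treatment continuing in the meantime. It adds: "Best overall response (BOR) will therefore include responses occurring at any time before disease progression and after early progression". Section 9.1.6 also asks for apparent progression to be confirmed after 4 weeks when there are no symptoms of clinical deterioration, and it sets no Week 12 limit.

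On scan timing, Section 8.3 says: "Subsequent assessments will be conducted at Week 12 in Cycle 1, followed by assessment every 12 weeks". Table 5 and Section 8.1 agree, with a window of ±1 week. No tumor imaging is scheduled between baseline and that assessment.

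The interval to the repeat scan is given in two ways. Section 8.3 says apparent early progression "should be confirmed 3 to 4 weeks later"; the imaging footnote to Table 5 says it "should be confirmed ≥4 weeks later", as does Section 8.1. Table 6 footnote a and Section 9.1.12 also require at least 4 weeks.

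**The concern.** irRECIST is used here because a response may follow an initial increase in tumor burden, as Section 9.1.12 explains. Whether that pattern can count in irBOR depends on how irPD at the first on-study scan is handled, and on that scan the two rules disagree. Footnote a keeps best response open until the repeat scan. Section 9.1.11, read literally, closes it at Week 12.

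The irRECIST response rate and stable disease rate in Section 14.5.5 would then depend on which section the programmer follows. In an open-label trial, leaving that choice until scans have been read allows the responder definition to be picked with the results in view.

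**Working it through.** The plan states no figure on this point, so there is none to reproduce. The check sets the two rules against the scan calendar and then sizes the effect of one subject.

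**Calendar.** Inputs: first on-study scan at Week 12 ±1 week, then every 12 weeks (Table 5, Sections 8.1 and 8.3); repeat scan at least 4 weeks after the first irPD (Table 6 footnote a).

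- Scheduled scans: baseline, then Weeks 12, 24, 36 and so on. Number scheduled between baseline and the Week 12 assessment: 0.
- First scan window: 12 − 1 = Week 11 to 12 + 1 = Week 13.
- Earliest repeat scan: 11 + 4 = Week 15, 12 + 4 = Week 16 or 13 + 4 = Week 17. All fall after Section 9.1.11 has fixed irBOR as irPD.
- For the exemption to work with the Week 12 assessment as the repeat scan, irPD must first be seen on an unscheduled scan no later than 11 − 4 = Week 7, 12 − 4 = Week 8 or 13 − 4 = Week 9.
- End of Therapy imaging may fall before Week 12, but a subject who stops before completing a cycle is outside the efficacy population in Section 14.5.

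**Classification of the same subject under each rule.**

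| Week 12 scan | Repeat scan | irBOR, Section 9.1.11 as written | irBOR, Table 6 footnote a |
|---|---|---|---|
| irPD | irPD confirmed | irPD | irPD |
| irPD | irPR | irPD | irPR |
| irPD | irSD | irPD | irSD |

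The rules differ in the second and third rows only.

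**Size.** Section 14.5.5 defines the response rate as the proportion with irCR or irPR, and the stable disease rate as the proportion with irCR, irPR or irSD. One subject in the second row moves both rates by 1/n; one in the third row moves only the stable disease rate.

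- n = 15: 1/15 = 6.7 points
- n = 12: 1/12 = 8.3 points
- n = 6: 1/6 = 16.7 points

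The value 15 is the approximate number to be treated at the expanded dose level (Section 14.3). The efficacy denominator is the number who complete at least one cycle, so it may be smaller and the shift larger.

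Illustration, assuming one second-row subject among 15 and no other responders, with Clopper-Pearson 95% intervals: 0/15 = 0% (0 to 21.8%) under Section 9.1.11, against 1/15 = 6.7% (0.2 to 31.9%) under footnote a.

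**Repeat-scan interval.** An interval of 3 to 4 weeks and one of at least 4 weeks overlap only at exactly 4 weeks. A repeat scan at 3 weeks complies with Section 8.3 and with none of the other four places.

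**The case against.** The best defence is that an assessment of irPD in Section 9.1.11 means irPD established under Section 9.1.6, and so already confirmed. That reading would narrow the conflict, but Section 9.1.11 does not say confirmed. If unconfirmed irPD never counted, an exemption for early irPD would hardly be needed. Nor can the footnote be limited to scans before Week 12, because it covers irPD at the 12-week assessment in terms.

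It may also be said that amending footnote a would reconcile the text equally well, and that the change proposed here is the one that can raise the response rate. The second part is true. On the first, the documents lean towards the footnote: Section 9.1.6 calls for confirmation too, and Section 9.1.11 presents its early-progression rule as following the primary response definitions.

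Several stronger readings are tempting but unsupported:

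- A reader might infer that irRECIST PFS changes as well. Neither passage dates progression; PFS is defined separately in Section 14.5.5.
- A reader might see a further contradiction with Section 9.1.12. That section governs whether treatment continues after radiologic progression, not how irBOR is classified. Treating past irPD while counting irBOR conservatively is coherent.
- A reader might conclude that all allowance for pseudoprogression is lost. The counting of new measurable lesions in tumor burden and the handling of equivocal non-target progression are untouched. Only the irBOR exemption is restricted.
- A reader might think a scan in Week 11 escapes the rule. Within the ±1 week window it is itself the Week 12 assessment.

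**Conclusion.** The conflict holds and sits on the first scheduled on-study scan of the efficacy population. As written, the Section 9.1.11 exemption can operate only after an unscheduled earlier scan. That follows from the schedule; it is not an estimated frequency.

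Each subject with irPD at Week 12 and a later irCR or irPR moves the irRECIST response rate by 1/n: 6.7 points if n = 15, and more if fewer complete a cycle. A subject who becomes irSD changes only the stable disease rate. The documents give no rate of unconfirmed irPD, so neither the number of subjects affected nor the total bias can be stated.

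The stakes are moderate. The endpoints are secondary and descriptive, no test or escalation decision depends on them, and RECIST 1.1 results are reported as well. The interval mismatch in Section 8.3 is a separate, minor point and adds no weight to this one.

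**What to change.** Reword Section 9.1.11 to match Table 6 footnote a. irPD found up to and including the Week 12 assessment, without rapid clinical deterioration, should preclude a later irBOR of irCR, irPR or irSD only if the repeat scan confirms it. Remove the restriction that the rescuing response must come from the Week 12 assessment. The rule for irPD first found after that assessment can stay as it is. Present RECIST 1.1 results beside the irRECIST results.

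The cost is wording only: the repeat scan is already required, so no imaging is added. The downside is that the irRECIST response rate may be slightly more favourable, and the RECIST 1.1 results shown alongside let the reader judge that. Make the change before response data are reviewed.

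Separately, reconcile the interval to the repeat scan in Section 8.3 with Table 5, Section 8.1, Table 6 footnote a and Section 9.1.12, so that one interval applies throughout.
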